5.3.2 Eliciting Adverse Event Information

A consistent methodology of non-directive questioning should be adopted for eliciting adverse event information at all patient evaluation timepoints. Examples of non-directive questions include the following:

"How have you felt since your last office visit?"

"Have you had any new or changed health problems since you were last here?"

5.3.3 Assessment of Severity of Adverse Events

The WHO toxicity grading scale (see [Appendix 8](#)) will be used for assessing adverse event severity. [Table 2](#) will be used for assessing severity for adverse events that are not specifically listed in the WHO toxicity grading scale.

Table 2 Adverse Event Severity Grading Scale for Events Not Specifically Listed in WHO Toxicity Grading Scale

Grade	Severity
1	Mild; transient or mild discomfort (<48 hours); no medical intervention or therapy required
2	Moderate; mild to moderate limitation in activity; some assistance may be needed; no or minimal medical intervention or therapy required
3	Severe; marked limitation in activity; some assistance usually required; medical intervention or therapy required; hospitalization possible
4	Life-threatening; extreme limitation in activity; significant assistance required; significant medical intervention or therapy required, hospitalization or hospice care probable

Notes: Developed by the Division of Microbiology and Infectious Diseases.

Regardless of severity, some events may also meet seriousness criteria. Refer to definition of a serious adverse event (see Section [5.2.2](#)).

5.3.4 Assessment of Causality of Adverse Events

Investigators should use their knowledge of the patient, the circumstances surrounding the event, and an evaluation of any potential alternative causes to determine whether an adverse event is considered to be related to the study drug, indicating "yes" or "no" accordingly. The following guidance should be taken into consideration (see also [Table 3](#)):

- Temporal relationship of event onset to the initiation of study drug
- Course of the event, with special consideration of the effects of dose reduction, discontinuation of study drug, or reintroduction of study drug (as applicable)
- Known association of the event with the study drug or with similar treatments
- Known association of the event with the disease under study
- Presence of risk factors in the patient or use of concomitant medications known to increase the occurrence of the event
- Presence of non-treatment-related factors that are known to be associated with the occurrence of the event

Table 3 Causal Attribution Guidance

Is the adverse event suspected to be caused by the study drug on the basis of facts, evidence, science-based rationales, and clinical judgment?	
YES	There is a plausible temporal relationship between the onset of the adverse event and administration of the study drug, and the adverse event cannot be readily explained by the patient's clinical state, intercurrent illness, or concomitant therapies; and/or the adverse event follows a known pattern of response to the study drug; and/or the adverse event abates or resolves upon discontinuation of the study drug or dose reduction and, if applicable, reappears upon re-challenge.
NO	An adverse event will be considered related, unless it fulfills the criteria specified below. Evidence exists that the adverse event has an etiology other than the study drug (e.g., preexisting medical condition, underlying disease, intercurrent illness, or concomitant medication); and/or the adverse event has no plausible temporal relationship to administration of the study drug (e.g., cancer diagnosed 2 days after first dose of study drug).

For patients receiving combination therapy, causality will be assessed individually for each protocol-mandated therapy.

5.3.5 Procedures for Recording Adverse Events

Investigators should use correct medical terminology/concepts when recording adverse events on the Adverse Event eCRF. Avoid colloquialisms and abbreviations.

Only one adverse event term should be recorded in the event field on the Adverse Event eCRF.

5.3.5.1 Injection Reactions

Adverse events that occur during or within 24 hours after study drug administration and are judged to be related to study drug injection should be captured as a diagnosis (e.g., "injection-site reaction" or "anaphylactic reaction") on the Adverse Event eCRF. If possible, avoid ambiguous terms such as "systemic reaction." Associated signs and symptoms should be recorded on the dedicated eCRF. If a patient experiences both a local and systemic reaction to the same dose of study drug, each reaction should be recorded separately on the Adverse Event eCRF, with signs and symptoms also recorded separately on the dedicated eCRF. Refer to the eCRF completion guideline for details.

5.3.5.2 Major Adverse Cardiac Events

MACE (including death due to cardiovascular causes, non-fatal myocardial infarction, non-fatal stroke or transient ischemic attack, unstable angina or chest pain requiring hospitalization, coronary revascularization, and congestive heart failure requiring hospitalization) should be recorded on the Adverse Event eCRF. Associated details should be recorded on the appropriate MACE CRF.

5.3.5.3 Diagnosis versus Signs and Symptoms

For adverse events other than injection reactions (see Section 5.3.5.1), a diagnosis (if known) should be recorded on the Adverse Event eCRF rather than individual signs and symptoms (e.g., record only liver failure or hepatitis rather than jaundice, asterixis, and elevated transaminases). However, if a constellation of signs and/or symptoms cannot be medically characterized as a single diagnosis or syndrome at the time of reporting, each individual event should be recorded on the Adverse Event eCRF. If a diagnosis is subsequently established, all previously reported adverse events based on signs and symptoms should be nullified and replaced by one adverse event report based on the single diagnosis, with a starting date that corresponds to the starting date of the first symptom of the eventual diagnosis.

5.3.5.4 Adverse Events That Are Secondary to Other Events

In general, adverse events that are secondary to other events (e.g., cascade events or clinical sequelae) should be identified by their primary cause, with the exception of severe or serious secondary events. A medically significant secondary adverse event that is separated in time from the initiating event should be recorded as an independent event on the Adverse Event eCRF. For example:

- If vomiting results in mild dehydration with no additional treatment in a healthy adult, only vomiting should be reported on the eCRF.
- If vomiting results in severe dehydration, both events should be reported separately on the eCRF.
- If a severe gastrointestinal hemorrhage leads to renal failure, both events should be reported separately on the eCRF.
- If dizziness leads to a fall and consequent fracture, all three events should be reported separately on the eCRF.
- If neutropenia is accompanied by an infection, both events should be reported separately on the eCRF.

All adverse events should be recorded separately on the Adverse Event eCRF if it is unclear as to whether the events are associated.

5.3.5.5 Persistent or Recurrent Adverse Events

A persistent adverse event is one that extends continuously, without resolution, between patient evaluation timepoints. Such events should only be recorded once on the Adverse Event eCRF. The initial severity (intensity or grade) of the event will be recorded at the time the event is first reported. If a persistent adverse event becomes more severe, the most extreme severity should also be recorded on the Adverse Event eCRF. Details regarding any changes in severity, increases or decreases, will be captured on Adverse Event Intensity or Grade Changes eCRF. If the event becomes serious, it should be reported to the Sponsor immediately (i.e., no more than 24 hours after learning that the event became serious; see Section 5.4.2 for reporting instructions). The Adverse Event eCRF should be updated by changing the event from

"non-serious" to "serious," providing the date that the event became serious, and completing all data fields related to serious adverse events.

A recurrent adverse event is one that resolves between patient evaluation timepoints and subsequently recurs. Each recurrence of an adverse event should be recorded as a separate event on the Adverse Event eCRF.

5.3.5.6 Abnormal Laboratory Values

Not every laboratory abnormality qualifies as an adverse event. A laboratory test result must be reported as an adverse event if it meets any of the following criteria:

- Is accompanied by clinical symptoms
- Results in a change in study treatment (e.g., treatment interruption or treatment discontinuation)
- Results in a medical intervention (e.g., potassium supplementation for hypokalemia) or a change in concomitant therapy
- Is clinically significant in the investigator's judgment

It is the investigator's responsibility to review all laboratory findings. Medical and scientific judgment should be exercised in deciding whether an isolated laboratory abnormality should be classified as an adverse event.

If a clinically significant laboratory abnormality is a sign of a disease or syndrome (e.g., ALP and bilirubin $5 \times$ ULN associated with cholestasis), only the diagnosis (i.e., cholestasis) should be recorded on the Adverse Event eCRF.

If a clinically significant laboratory abnormality is not a sign of a disease or syndrome, the abnormality itself should be recorded on the Adverse Event eCRF, along with a descriptor indicating whether the test result is above or below the normal range (e.g., "elevated potassium," as opposed to "abnormal potassium"). If the laboratory abnormality can be characterized by a precise clinical term per standard definitions, the clinical term should be recorded as the adverse event. For example, an elevated serum potassium level of 7.0 mEq/L should be recorded as "hyperkalemia."

Observations of the same clinically significant laboratory abnormality from visit to visit should only be recorded once on the Adverse Event eCRF (see Section [5.3.5.5](#) for details on recording persistent adverse events).

5.3.5.7 Abnormal Vital Sign Values

Not every vital sign abnormality qualifies as an adverse event. A vital sign result must be reported as an adverse event if it meets any of the following criteria:

- Is accompanied by clinical symptoms
- Results in a change in study treatment (e.g., treatment interruption or treatment discontinuation)

- Results in a medical intervention or a change in concomitant therapy
- Is clinically significant in the investigator's judgment

It is the investigator's responsibility to review all vital sign findings. Medical and scientific judgment should be exercised in deciding whether an isolated vital sign abnormality should be classified as an adverse event.

If a clinically significant vital sign abnormality is a sign of a disease or syndrome (e.g., high blood pressure), only the diagnosis (i.e., hypertension) should be recorded on the Adverse Event eCRF.

Observations of the same clinically significant vital sign abnormality from visit to visit should only be recorded once on the Adverse Event eCRF (see Section [5.3.5.5](#) for details on recording persistent adverse events).

5.3.5.8 Abnormal Liver Function Tests

The finding of an elevated ALT or AST ($>3 \times \text{ULN}$) in combination with either an elevated total bilirubin ($>2 \times \text{ULN}$) or clinical jaundice in the absence of cholestasis or other causes of hyperbilirubinemia is considered to be an indicator of severe liver injury (as defined by Hy's Law). Therefore, investigators must report as an adverse event the occurrence of either of the following:

- Treatment-emergent ALT or AST $>3 \times \text{ULN}$ in combination with total bilirubin $>2 \times \text{ULN}$
- Treatment-emergent ALT or AST $>3 \times \text{ULN}$ in combination with clinical jaundice

The most appropriate diagnosis or (if a diagnosis cannot be established) the abnormal laboratory values should be recorded on the Adverse Event eCRF (see Section [5.3.5.3](#)) and reported to the Sponsor immediately (i.e., no more than 24 hours after learning of the event), either as a serious adverse event or an adverse event of special interest (see Section [5.4.2](#)).

5.3.5.9 Deaths

All deaths that occur during the protocol-specified adverse event reporting period (see Section [5.3.1](#)), regardless of relationship to study drug, must be recorded on the Adverse Event eCRF and immediately reported to the Sponsor (see Section [5.4.2](#)).

Death should be considered an outcome and not a distinct event. The event or condition that caused or contributed to the fatal outcome should be recorded as the single medical concept on the Adverse Event eCRF. Generally, only one such event should be reported. If the cause of death is unknown and cannot be ascertained at the time of reporting, "**unexplained death**" should be recorded on the Adverse Event eCRF. If the cause of death later becomes available (e.g., after autopsy), "unexplained death" should be replaced by the established cause of death. The term "**sudden death**" should not be used unless combined with the presumed cause of death (e.g., "sudden cardiac death").

Deaths that occur after the adverse event reporting period should be reported as described in Section 5.6.

5.3.5.10 Preexisting Medical Conditions

A preexisting medical condition is one that is present at the screening visit for this study. Such conditions should be recorded on the General Medical History and Baseline Conditions eCRF.

A preexisting medical condition should be recorded as an adverse event only if the frequency, severity, or character of the condition worsens during the study. When recording such events on the Adverse Event eCRF, it is important to convey the concept that the preexisting condition has changed by including applicable descriptors (e.g., "more frequent headaches").

5.3.5.11 Lack of Efficacy or Worsening of Atopic Dermatitis

Medical occurrences or symptoms of deterioration that are anticipated as part of AD should be recorded as an adverse event if judged by the investigator to have unexpectedly worsened in severity or frequency or changed in nature at any time during the study. When recording an unanticipated worsening of AD on the Adverse Event eCRF, it is important to convey the concept that the condition has changed by including applicable descriptors (e.g., "accelerated worsening of atopic dermatitis").

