3.1.1 Internal Monitoring Committee

An Internal Monitoring Committee (IMC) will monitor data on safety and study conduct on an ongoing basis. Members of the IMC will be unblinded and will include representatives from Clinical Science and Drug Safety who are not directly involved in the study and representatives from Biostatistics and Statistical Programming and Analysis. Further details regarding roles and responsibilities will be outlined in the IMC Charter.

The IMC will review cumulative data at regular intervals of approximately every 3 months from the time of randomization of the first patient. Ad hoc meetings may be held at the request of the IMC or Sponsor at any time to address potential safety concerns. The data to be reviewed will include demographics, concomitant medications, study drug administration, adverse events, serious adverse events, adverse events of special interest, ECGs, and relevant laboratory data.

At the time of each review, the IMC will make one of the following recommendations: the trial continues as planned, the trial is stopped for safety reasons, the protocol is amended, additional analyses need to be performed, or enrollment will be held pending further safety evaluations. Decisions will be made in consideration of the totality of the available data. Final decisions will rest with the Sponsor's study team.

Any outcomes of these reviews that affect study conduct will be communicated in a timely manner to the investigators for notification of their respective Institutional Review Board (IRB) or Ethics Committee (EC).

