5.2.1 Adverse Events

According to the ICH guideline for Good Clinical Practice, an adverse event is any untoward medical occurrence in a clinical investigation subject administered a pharmaceutical product, regardless of causal attribution. An adverse event can therefore be any of the following:

- Any unfavorable and unintended sign (including an abnormal laboratory finding), symptom, or disease temporally associated with the use of a medicinal product, whether or not considered related to the medicinal product
- Any new disease or exacerbation of an existing disease (a worsening in the character, frequency, or severity of a known condition) (see Sections [5.3.5.10](#) and [5.3.5.11](#) for more information)
- Recurrence of an intermittent medical condition (e.g., headache) not present at baseline
- Any deterioration in a laboratory value or other clinical test (e.g., ECG, X-ray) that is associated with symptoms or leads to a change in study treatment or concomitant treatment or discontinuation from study drug
- Adverse events that are related to a protocol-mandated intervention, including those that occur prior to assignment of study treatment (e.g., screening invasive procedures such as biopsies)

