5.2.2 Serious Adverse Events (Immediately Reportable to the Sponsor)

A serious adverse event is any adverse event that meets any of the following criteria:

- Is fatal (i.e., the adverse event actually causes or leads to death)
- Is life threatening (i.e., the adverse event, in the view of the investigator, places the patient at immediate risk of death)

This does not include any adverse event that, had it occurred in a more severe form or was allowed to continue, might have caused death.

- Requires or prolongs inpatient hospitalization (see Section [5.3.5.12](#))

- Results in persistent or significant disability/incapacity (i.e., the adverse event results in substantial disruption of the patient's ability to conduct normal life functions)
- Is a congenital anomaly/birth defect in a neonate/infant born to a mother exposed to study drug
- Is a significant medical event in the investigator's judgment (e.g., may jeopardize the patient or may require medical/surgical intervention to prevent one of the outcomes listed above)

The terms "severe" and "serious" are not synonymous. Severity refers to the intensity of an adverse event (e.g., rated as mild, moderate, severe, or life-threatening according to WHO Adverse Drug Reaction Terminology; see Section 5.3.3); the event itself may be of relatively minor medical significance (such as severe headache without any further findings).

Severity and seriousness need to be independently assessed for each adverse event recorded on the eCRF.

Serious adverse events are required to be reported by the investigator to the Sponsor immediately (i.e., no more than 24 hours after learning of the event; see Section 5.4.2 for reporting instructions).

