5.3.5.12 Hospitalization or Prolonged Hospitalization

Any adverse event that results in hospitalization (i.e., inpatient admission to a hospital) or prolonged hospitalization should be documented and reported as a serious adverse event (per the definition of serious adverse event in Section 5.2.2), except as outlined below.

An event that leads to hospitalization under the following circumstances should not be reported as an adverse event or a serious adverse event:

- Hospitalization for a preexisting condition, provided that all of the following criteria are met:

The hospitalization was planned prior to the study or was scheduled during the study when elective surgery became necessary

The patient has not experienced an adverse event

An event that leads to hospitalization under the following circumstances is not considered to be a serious adverse event, but should be reported as an adverse event instead:

- Hospitalization that was necessary because of patient requirement for outpatient care outside of normal outpatient clinic operating hours

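### Section 5.3.5.11 can be read to exclude anticipated worsening of atopic dermatitis from adverse events, in conflict with 5.2.1 and 5.3.5.10, so a serious flare could miss SAE reporting

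*Combined protocol and SAP*

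**What the plan says.** Section 5.3.5.11 is the only recording rule specific to the disease under study. It says that anticipated symptoms of deterioration "should be recorded as an adverse event if judged by the investigator to have unexpectedly worsened in severity or frequency or changed in nature". Its next sentence, on descriptors, addresses one case only: "When recording an unanticipated worsening of AD on the Adverse Event eCRF".

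Two neighbouring rules contain no test of expectedness:

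- Section 5.2.1 includes among adverse events "Any new disease or exacerbation of an existing disease (a worsening in the character, frequency, or severity of a known condition"), and refers to 5.3.5.10 and 5.3.5.11 for further detail.
- Section 5.3.5.10 records a preexisting condition as an adverse event "only if the frequency, severity, or character of the condition worsens during the study".

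The rules on seriousness come after these. Section 5.2.2 begins "A serious adverse event is any adverse event that meets any of the following criteria", and 5.3.5.12 covers "Any adverse event that results in hospitalization (i.e., inpatient admission to a hospital) or prolonged hospitalization". Section 6.5 summarises serious adverse events, and adverse events that led to stopping study drug or leaving the study. For the IMC, section 3.1.1 states: "The data to be reviewed will include demographics, concomitant medications, study drug administration, adverse events, serious adverse events, adverse events of special interest, ECGs", plus relevant laboratory data. No efficacy score is on that list.

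**The concern.** The trial enrols patients with moderate to severe AD and withholds topical corticosteroids and calcineurin inhibitors except as rescue (4.3.4, 4.4.2). An investigator could readily call a flare anticipated in that setting. If 5.3.5.11 then decides whether the flare is an adverse event at all, everything downstream depends on each investigator's view of what was to be expected.

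Whether a new agent worsens the disease it is meant to treat is a central safety question. The efficacy scales cannot fill the gap on the safety side: section 4.5.9 says that the Sponsor will not derive adverse event reports from patient- or clinician-reported outcomes and will not use those data in safety analyses. AD worsening is not among the adverse events of special interest in 5.2.3, so that route to a 24-hour report is also closed.

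**Working it through.** The question is one of text, so the check sets the sections side by side and follows a single event through them: a flare that the investigator judges anticipated and unchanged in nature, and that leads to an unplanned admission.

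**Step 1. Is it an adverse event?**

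| Section | Rule | Result for this flare |
|---|---|---|
| 5.2.1 | Exacerbation of an existing disease | Adverse event |
| 5.3.5.10 | Worsening of a preexisting condition | Adverse event |
| 5.3.5.11 | AD deterioration, if unexpectedly worse or changed in nature | Not an adverse event, if the condition is read as exclusive |

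Two features favour the exclusive reading of 5.3.5.11. Its descriptor sentence speaks only of unanticipated worsening, and the word *unexpectedly* would do no work if all AD worsening were already covered. Two features count against it. The section says *if*, whereas 5.3.5.10 says *only if*; and 5.2.1 cites it for information, not as an exception. The text does not settle the matter.

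**Step 2. Does admission restore it?** Sections 5.2.2 and 5.3.5.12 both apply to an adverse event that already exists. The exemption in 5.3.5.12 for preexisting conditions covers only admissions that were planned or elective and involved no adverse event. This admission is not exempt, but no sentence makes it an adverse event either. The result follows Step 1.

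**Step 3. Is there an override?** For laboratory and vital-sign findings there is one: 5.3.5.6 and 5.3.5.7 make them adverse events if they change study treatment or lead to medical intervention. Section 5.3.5.11 has no counterpart.

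**Step 4. What is lost on the restrictive reading, and what remains?**

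| Item | Source | Captured? |
|---|---|---|
| 24-hour SAE report | 5.2.2, 5.4.2 | No |
| SAE summary | 6.5 | No |
| Summary of adverse events leading to stopping study drug, if the flare does so | 6.5 | No |
| IMC adverse event and SAE data | 3.1.1 | No |
| Reason for stopping study drug | 4.6.1, 6.2 | Yes |
| Treatment failure | 4.3.4, 6.2 | Yes, if rescue was given in the treatment period |
| Rescue medication and dosing, as seen by the IMC | 3.1.1, 4.4 | Yes, but not as an admission or a serious event |

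**Step 5. Size.** About 90 patients randomized 1:1 gives 90/2 = 45 per arm. One unrecorded event is 1/45 = 0.022, or 2.2 percentage points of an arm's SAE incidence, assuming that all 45 are dosed and that the patient has no other SAE. The documents give no rate of flares, flare admissions or flare-related discontinuations, so the number of missed events cannot be derived.

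**The case against.** The strongest case on the other side is that the documents do not exclude anticipated flares. Section 5.3.5.11 never says *only if*, and the section just before it shows that the drafters used that phrase when they meant it. Section 5.2.1 makes any exacerbation an adverse event, and under it an unplanned flare admission would be an SAE. A change in nature qualifies without any test of expectedness. A flare bad enough for admission is also the one an investigator is most likely to judge unexpectedly severe. All of this stands. A reader might infer that the plan definitively removes hospitalizing flares from safety reporting; the text supports only an unresolved conflict that sites may settle differently.

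A reader might also infer that flares which stop study drug vanish from the discontinuation data, or that the IMC could not see them. Neither is supported. The primary reason for every treatment discontinuation goes on the eCRF (4.6.1) and is listed and summarised with treatment failure (6.2). The unblinded IMC receives concomitant medications and study drug administration about every 3 months and can ask for further analyses. The exposed items are the adverse-event-based summaries in 6.5, the SAE reporting route and the adverse event data within the IMC package.

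Finally, separating expected disease fluctuation from adverse events is a reasonable choice. If the drug works, recording every systemic rescue as an adverse event would load efficacy failures onto the placebo arm's safety profile. That also stands, and it limits how far the fix should go.

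**Conclusion.** The concern holds as a conflict between sections with a specific consequence. On one plausible reading of 5.3.5.11, an anticipated flare that meets a seriousness criterion is never recorded as an adverse event, and no sentence corrects this. On the other reading it is an SAE. The protocol should not leave that to each site.

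The effect on the results cannot be sized beyond 2.2 points per missed event in a 45-patient arm. Any larger figure would rest on an assumed count. If equal numbers were missed in equal-sized arms, the between-arm difference would not change, but both arms' SAE rates would be understated and the individual 24-hour reports would still be missing. The conclusion depends on no power or effect-size assumption, only on how the sections fit together.

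**What to change.** Reconcile 5.3.5.11 with 5.2.1, 5.3.5.10 and 5.3.5.12 by adding one sentence to 5.3.5.11, for example: *Any worsening of AD that meets a seriousness criterion in Section 5.2.2 is recorded as an adverse event and reported as a serious adverse event, whether or not it was anticipated.* State in the same place that the expectedness filter applies to non-serious worsening only, so that 5.2.1 and 5.3.5.10 no longer pull the other way.

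Do not extend the sentence to every use of systemic rescue. A non-serious anticipated flare that stops study drug would then still be absent from the 6.5 summary, but 6.2 would show the reason for stopping.

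The cost is one sentence of protocol text and a few more SAE reports that overlap with efficacy failure. Clinical management and the efficacy analysis are unchanged.
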